8.3.1. Time Period and Frequency for Collecting AE and SAE Information

Monitoring and recording of AEs and SAEs will be conducted throughout the study. After the signing of the ICF, but prior to initiation of study treatment, only SAEs caused by a protocol-mandated treatment will be collected (eg, SAEs related to invasive procedures, such as biopsies or medication washout). Any medical occurrence that begins before the start of study treatment but after obtaining informed consent, and which is not considered an SAE caused by a protocol-mandated treatment, will be recorded on the Medical History/Current Medical Conditions Section of the eCRF rather than the AE section.

All AEs and SAEs will be collected from the start of treatment until 30 days after the last dose, or upon initiation of alternative cancer treatment, whichever occurs first. After this period, investigators should report only SAEs that are thought to be related to RMC-4630 and/or sotorasib.

Any SAE that is determined to be study-treatment related (possibly, probably, or definitely related) will be followed to resolution or stabilization, until it is determined to be irreversible by the investigator, the subject is lost to follow-up, or it has been determined that the study treatment is not the cause of the AE/SAE, whichever occurs first. After this period, investigators should report only SAEs that are thought to be related to RMC-4630 and/or sotorasib.

All SAEs will be recorded and reported to the Sponsor or designee within 24 hours of investigator awareness, as indicated in [Appendix 3](#). The investigator will submit any updated SAE data to the Sponsor within 24 hours of it being available. During the Extended-Use phase of the study, only SAEs (irrespective of causality) and related AEs will be reported in the EDC. All SAEs will also be reported on the SAE Report Form.

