2.2.4 Duration and End of Study (EOS)

The study duration is approximately 2 years. The EOS is defined as the date of LSLV or 12 months after the last subject receives the first dose of study treatment, whichever occurs first.

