7.7 Safety Analyses

Safety endpoints of the study are the incidence, nature, and severity of treatment-emergent adverse events (TEAEs), SAEs, clinical laboratory tests, vital signs, and ECGs.

Adverse events (AEs) will be collected from the date that informed consent was signed. Verbatim terms for each AE will be coded using MedDRA Version 25.0 or later and graded per the NCI CTCAE Version 5.0 or later. Treatment-emergent adverse event (TEAE) is defined as those AEs with an onset on or after the date of the first dose of study intervention and within 30 days of last known dose of study intervention. Treatment-related AEs are treatment-emergent AEs reported as related to RMC-4630 or sotorasib.

All AE summaries will be presented for the initial combination dose level and overall using the treated population.

Safety Stopping Rules

During dose expansion after the final expansion dose has been selected, evaluation of all Grade 4 or higher treatment-related adverse event rates will be conducted to assess if the unacceptable toxicity threshold has been reached. If this threshold is met, enrollment to dose expansion will be halted pending review of safety data. After reviewing the totality of data from both CodeBreaK 101C and cumulative data from this study, one of the following actions may be taken:

1. Terminate the study
2. Amend the protocol to potentially improve the benefit/risk for subjects (e.g., increase safety monitoring, modify dose/schedule, mandate premedication)
3. Continue dose expansion without any changes

The stopping rules use a Bayesian approach to pause the enrollment if the posterior probability is $\geq 80\%$ that the Grade 4 or higher treatment-related adverse event rate is greater than 20%. The stopping boundaries shown in Table 1 assume a prior distribution of Beta (0.4, 1.6). The operating characteristics with the pre-specified batch size of 10 new subjects are summarized in Table 2.

Table 1: Stopping Boundary by Number of Subjects

Number of Subjects Treated	Number if Subjects with Grade 4 or Higher Treatment Related Adverse Events to Halt Enrollment
10	≥ 4
20	≥ 6
30	≥ 9
40	Expansion Complete

Table 2: Operating Characteristics of Stopping Rules

True Grade 4 or Higher Treatment-Related Adverse Event Rate	Probability of Early Stopping of Dose Expansion	Average Dose Expansion Sample Size
0.1	2.1%	39
0.15	9.7%	38
0.2	25.8%	34
0.25	47.7%	29
0.3	69.2%	23

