7.7.3 Adverse Events

The overview summary will include number of events; number and percentage of participants for categories of AEs; grade ≥ 3 TEAEs, treatment-related AEs, grade ≥ 3 treatment-related TEAEs, SAEs, treatment-related SAEs, AEs leading to study drug discontinuation, dose level reduction, interruption, or dose change, adverse events of clinical interests (ECI), and AEs leading to death.

The number and percentage of subjects who experienced AEs will also be summarized by preferred term (PT) by descending order of incidence of PT. In addition, AEs and SAEs will also be summarized by system organ class (SOC) and PT by descending order of incidence of SOC, and descending order of incidence of PT within each SOC. The summaries will include the following for any grade and grade ≥ 3 if applicable:

- Overview Summary of TEAEs
- Summary of TEAEs by SOC and PT
- Summary of TEAEs by PT
- Summary of TEAEs related to RMC-4630 by PT
- Summary of TEAEs related to sotorasib by PT
- Summary of TEAEs related to RMC-4630 or sotorasib by PT
- Summary of TEAEs by maximum severity and PT
- Summary of TEAEs related to RMC-4630 or sotorasib by maximum severity and PT
- Summary of serious TEAEs by SOC and PT
- Summary of non-Serious TEAEs by SOC and PT

- Summary of serious TEAEs by PT
- Summary of serious TEAEs related to RMC-4630 by PT
- Summary of serious TEAEs related to sotorasib by PT
- Summary of serious TEAEs related to RMC-4630 or sotorasib by PT
- Summary of TEAEs leading to discontinuation of RMC-4630 by PT
- Summary of TEAEs leading to discontinuation of sotorasib by PT
- Summary of TEAEs leading to discontinuation of RMC-4630 or sotorasib by PT
- Summary of TEAEs leading to discontinuation of RMC-4630 or sotorasib by SOC and PT
- Summary of TEAEs leading to dose reduction of RMC-4630 by PT
- Summary of TEAEs leading to dose reduction of sotorasib by PT
- Summary of TEAEs leading to reduction of RMC-4630 or sotorasib and PT
- Summary of TEAEs leading to reduction of RMC-4630 or sotorasib by SOC and PT
- Summary of TEAEs leading to dose interruption of RMC-4630 by PT
- Summary of TEAEs leading to dose interruption of sotorasib by PT
- Summary of TEAEs leading to dose interruption of RMC-4630 or sotorasib by PT
- Summary of TEAEs leading to dose interruption of RMC-4630 or sotorasib by SOC and PT
- Summary of TEAEs leading to dose modification of RMC-4630 by PT
- Summary of TEAEs leading to dose modification of RMC-4630 by SOC and PT

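### AE percentages by initial dose level are not adjusted for differing exposure or follow-up; exposure-adjusted and common-window incidence for the key AE categories would be a cheap addition

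*SAP*

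**What the plan says.** **Measure and grouping.** SAP 7.7: "All AE summaries will be presented for the initial combination dose level and overall using the treated population". SAP 7.7.3: "The number and percentage of subjects who experienced AEs will also be summarized by preferred term (PT) by descending order of incidence of PT". The overview table adds a number of events, without person-time. Duration of exposure (SAP 7.5) and time on each treatment (SAP 7.2) are summarised on their own. Time to onset is planned for events of clinical interest and some haematologic abnormalities (SAP 7.7.1), as descriptive statistics only.

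**Window per subject.** The SAP counts as treatment-emergent any AE with "onset on or after the date of the first dose of study intervention and within 30 days of last known dose of study intervention". Protocol 8.3.1 collects all AEs "until 30 days after the last dose, or upon initiation of alternative cancer treatment, whichever occurs first".

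**Calendar limits.** SAP 2.2.4: "The study duration is approximately 2 years" and "The EOS is defined as the date of LSLV or 12 months after the last subject receives the first dose of study treatment", whichever comes first. For subjects who continue beyond that point, Protocol 8.3.1 says: "During the Extended-Use phase of the study, only SAEs (irrespective of causality) and related AEs will be reported in the EDC".

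**Order of enrolment.** SAP 2.3 plans up to 6 subjects at RMC-4630 140 mg, then 6 more at 200 mg if escalation is decided. Under SAP 2.2.1, sotorasib 240 mg as an initial dose applies to new subjects only. The same section lets one or both levels enrol further subjects after the run-in, and lets the sponsor go to expansion without completing the run-in.

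**The concern.** A crude percentage of subjects with an AE depends on the event rate and on how long subjects were at risk and observed. If two dose levels differ in the second, their percentages can differ with no difference in toxicity, or agree when there is one. The plan gives three reasons to expect differing observation: sequential opening of RMC-4630 levels, a later sotorasib level restricted to new subjects, and reduced AE collection after main EOS for those still on drug.

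Protocol 2.2.2.3 itself warns that AEs of the combination may become more frequent and more severe the longer treatment lasts, so duration is not a side issue here. At stake is the side-by-side safety display by dose. It supports the description of benefit and risk at the final dose and, at any earlier data cut, could inform the choice of expansion dose, which SAP 2.2.1 bases partly on cumulative data from this study.

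**Working it through.** **1. The plan's own AE figure.** SAP 2.3 says 46 subjects give at least 90% probability of seeing an AE of 5% incidence. 1 − 0.95^46 = 0.906, so this reproduces. It is the only planning figure on AE incidence and does not involve exposure.

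**2. Inputs and assumptions.**
- Potential follow-up C: a study of about 24 months, with EOS at the 12-month limit, leaves about 24 − 12 = 12 months for accrual. The first subject then has about 24 months and the last about 12. Less extreme pairs are assumed to represent whole levels.
- Time on treatment T: the documents give none for the combination. I use an exponential with median m = 6.3 months, the sotorasib monotherapy PFS median in Protocol 2.1.2, and vary m from 4 to 10.
- AE hazard h: constant and equal at both levels, 0.01 to 0.5 per month (assumption).

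**3. Formulas.** λ = ln 2 / m = 0.110 per month at m = 6.3.
- Still on drug at the cut: exp(−λC).
- Mean on-treatment time: (1 − exp(−λC)) / λ.
- Subject incidence with window min(T + 1 month, C): P = 1 − { e^(−h) · λ/(λ+h) · [1 − e^(−(λ+h)(C−1))] + e^(−λ(C−1)) · e^(−hC) }.

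**4. Final analysis, m = 6.3, h = 0.05.**
- C = 24: P = 1 − (0.6375 + 0.0240) = 33.8%.
- C = 12: P = 1 − (0.5415 + 0.1636) = 29.5%.

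| Early / late C (months) | Still on drug at cut | Mean time on drug (months) | Crude AE % | Difference (points) |
|---|---|---|---|---|
| 24 / 12 (first vs last subject) | 7.1% / 26.7% | 8.44 / 6.66 | 33.8 / 29.5 | 4.4 |
| 20 / 14 | 11.1% / 21.4% | 8.08 / 7.14 | 33.2 / 30.9 | 2.3 |
| 22 / 16 | 8.9% / 17.2% | 8.28 / 7.53 | 33.6 / 31.9 | 1.7 |
| 24 / 18 | 7.1% / 13.8% | 8.44 / 7.83 | 33.8 / 32.6 | 1.2 |

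Differences are taken before rounding. Of the hazards tried, 0.05 gives the largest gap. At h = 0.5 the gap is 0.1 points or less. For 24 / 12 the largest gap is 1.7 points at m = 4 and 8.2 points at m = 10.

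**5. Earlier cut, m = 6.3, h = 0.10.** The simpler on-treatment form is P = h/(h+λ) · [1 − e^(−(h+λ)C)], with h/(h+λ) = 0.476. The cut times are assumed.
- 5 vs 2 months: 0.476 × 0.650 = 31% vs 0.476 × 0.343 = 16%.
- 4 vs 2 months: 27% vs 16%.
- 6 vs 3 months: 34% vs 22%.

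Including the 30-day tail, 5 vs 2 months gives 34% vs 18%.

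**6. Direction.** Keep h = 0.05 at both levels but let the later level stay on drug longer (median 10 vs 6.3 months). The crude figures are 33.8% early vs 34.0% late at 24 / 12, and 33.6% vs 38.1% at 22 / 16. The sign reverses.

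**7. Sampling error.** For a 30% rate, √(0.3 × 0.7 / 6) = 18.7 points with 6 subjects, and 7.2 points with 40.

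**The case against.** Several stronger readings are tempting, and the documents do not support them.

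- **That all full AE collection stops on one calendar date.** A reader might infer this from the EOS definition. But each subject's window closes 30 days after the last dose or at new anticancer therapy, so the calendar cut touches essentially only subjects still on drug or in that tail. If the last visit triggers EOS first, almost nobody is left to truncate.
- **That the earlier level will look more toxic.** This needs equal time on treatment at both levels. Step 6 shows that it can reverse. The 24 versus 12 months contrast is also between the first and last subjects, not between levels. Levels may enrol together, the run-in may be skipped, and one level can hold both the earliest and the latest subjects.
- **That the SAP compares levels, or that its final tables choose the dose.** No test or between-level comparison is specified. Escalation follows DLTs in a fixed 21-day window, the sponsor selects the expansion dose on the totality of data including CodeBreaK 101C, and the final analysis comes after that choice.

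It is also fair to say that exposure is already reported by level, so a reader can see an imbalance, and that at final analysis the distortion is far below the sampling error of a 6-subject level.

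All of this limits the size and certainty of the point. It does not supply the missing measure. Separate exposure tables do not let a reader convert a crude percentage into a rate for a given AE category. SAP section 8 permits analyses during the study, when follow-up between levels may be most unequal. A distortion whose sign cannot be stated in advance is a reason to adjust for it.

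**Conclusion.** The point holds in a limited form. By-dose AE percentages are unadjusted for exposure and follow-up, and neither document plans an alternative beyond the DLT window. At final analysis the follow-up effect is about 2 to 4 percentage points at a 6.3-month median time on treatment (1.2 in the mildest timing tried) and up to about 8 at 10 months. It is near zero for common, early-onset AEs. At an earlier cut it could reach 11 to 15 points, but only under assumed follow-up times that the documents do not give. The net direction is not fixed.

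These figures rest on exponential time on treatment, a monotherapy PFS median as proxy, and a constant hazard equal at both levels. If hazards rise with duration, as Protocol 2.2.2.3 allows, the constant-hazard figures may understate the effect. This is a worthwhile, inexpensive improvement to a descriptive display and does not invalidate the safety analysis.

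A related gap is that the SAP was written for Protocol V4.0 and describes a separate extended-use or roll-over study. The current protocol keeps Extended-Use within the study under narrower AE reporting. The SAP does not say whether doses and events in that phase count toward its treatment-emergent window.

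**What to change.** In SAP 7.7.3, for the overview categories only (any TEAE, Grade ≥3, treatment-related, serious, events of clinical interest), add by initial combination dose level:

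1. Exposure-adjusted incidence: subjects with the event divided by subject-months to first event or to the end of the treatment-emergent period.
2. Incidence within a common window, among subjects who had the opportunity to complete it. This could be the first 2 cycles (42 days), or cumulative incidence at a common time of 12 months or less.

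State that dose levels are read side by side on these two measures, including at any cut made during the study, and keep the crude percentages as description. Update the SAP to the current protocol: cut these tables at main EOS and list Extended-Use events separately, since only SAEs and related AEs are recorded there.

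The cost is SAP wording, some programming from dates already collected, and a few extra columns. The rates assume a roughly constant hazard and will be imprecise at a level with about 6 subjects. A short common window leaves out later-onset events. The two measures are paired because each covers the other's weakness.

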2.3 Sample Size Determination

Up to a total of 46 subjects will be enrolled into this study. Approximately 6 to 12 subjects will be enrolled during the safety run-in portion of the study. Initially, up to 6 subjects will be enrolled and treated at the dose of 140 mg BIW on D1D2 of each week in a 21-day cycle (i.e., Days 1, 2, 8, 9, 15, and 16 of each 21-day cycle) in combination with sotorasib at 960 mg QD. An additional 6 subjects may be enrolled to receive RMC-4630 200 mg BIW on D1D2 of each week in a 21-day cycle (i.e., Days 1, 2, 8, 9, 15, and 16 of each 21-day cycle) in combination with sotorasib at 960 mg QD, if a decision is made to increase the RMC-4630 dose from 140 mg to 200 mg. After completion of the safety run-in (DLT clearance) of both dose levels, additional patients may be enrolled for the purpose of dose optimization to inform the selection of the final expansion dose. Expansion may commence as soon as the final expansion dose has been selected. Approximately 34 to 40 subjects will be enrolled for dose optimization and dose expansion.

With a total sample size of 46 subjects, the probability of observing at least 1 AE with an incidence rate of 5% is at least 90%.

The ORR will be reported by dose level pooling subjects from safety run-in and dose optimization (if applicable) and expansion. It's anticipated that approximately 20 to 40 subjects will be treated at the final expansion dose depending on the actual number of subjects enrolled during safety run-in and/or dose optimization. For the final expansion dose, with 20 and 40 subjects, the lower bound of the one-sided 80% exact CI will be above 33.7% and 37.3% respectively if the observed response rate is 45%.

The mutational status of each subject and, thus, placement into Cohort 1 or 2 (Protocol Section 4.1) will be determined based on the historic genomic reports and later might be adjusted based on ctDNA analysis results collected at baseline. Therefore, the sample size for one or both cohorts will depend on the distribution of mutational status.

3. Endpoints

Primary Endpoints

- ORR as assessed per RECIST v1.1

Secondary Endpoints

- Incidence, nature, and severity of TEAEs, SAEs, clinically significant changes in laboratory tests, ECGs, and vital signs
- Trough and approximate peak concentrations of RMC-4630 and sotorasib
- DOR, DCR, and PFS as assessed per RECIST v1.1, and OS

Exploratory Endpoints

- Sotorasib and RMC-4630 exposure/safety and exposure/efficacy relationships

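### Do the safety stopping rule's operating characteristics mislead because they are given only for an expansion of 40 subjects?

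*SAP*

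**What the plan says.** The rule is in SAP 7.7 (Safety Stopping Rules), repeated in Protocol 9.4.2. It applies "During dose expansion after the final expansion dose has been selected". Enrolment pauses if the posterior probability that the Grade 4 or higher treatment-related event rate exceeds 20% is at least 80%, under a Beta(0.4, 1.6) prior. Table 1 of that section gives the boundaries against a column headed "Number of Subjects Treated": at least 4 of 10, 6 of 20 and 9 of 30. Its row for 40 reads "Expansion Complete". On crossing, "enrollment to dose expansion will be halted pending review of safety data"; the sponsor may then terminate, amend or continue unchanged.

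On performance, SAP 7.7 says: "The operating characteristics with the pre-specified batch size of 10 new subjects are summarized in Table 2". Table 2 gives pause probabilities of 2.1 / 9.7 / 25.8 / 47.7 / 69.2% at true rates 0.10 / 0.15 / 0.20 / 0.25 / 0.30, with average sizes 39 / 38 / 34 / 29 / 23.

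SAP 2.3 supplies the sizes. "Approximately 34 to 40 subjects will be enrolled for dose optimization and dose expansion", out of a total of up to 46. In its paragraph on ORR, which pools run-in, optimization and expansion by dose level, it anticipates that "approximately 20 to 40 subjects will be treated at the final expansion dose".

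**The concern.** A look can pause enrolment only while subjects remain to be enrolled. Table 2 assumes 40 subjects, and 40 is the top of the range in SAP 2.3. That section takes 20 as a design point for response-rate precision ("For the final expansion dose, with 20 and 40 subjects, the lower bound of the one-sided 80% exact CI"), yet the safety rule has no figures for 20. If dose optimization uses part of the shared pool of 34 to 40, expansion could end before the look at 30, or even before the look at 20 could act. A safety committee relying on Table 2 would expect about seven chances in ten of a pause at a true rate of 0.30, when the real chance might be nearer one in three. Table 2 is also the plan's only statement of how often the rule acts.

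**Working it through.** **Inputs.** Prior Beta(0.4, 1.6), rate threshold 0.20, posterior threshold 0.80, batches of 10 and expansion complete at 40 (SAP 7.7); 46 in total, 6 to 12 in run-in, and 34 to 40 in optimization plus expansion (SAP 2.3).

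**Boundaries.** The smallest r with P(rate > 0.20 | Beta(0.4 + r, 1.6 + n − r)) ≥ 0.80:

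- n = 10: r = 4 gives 0.895; r = 3 gives 0.720.
- n = 20: r = 6 gives 0.826; r = 5 gives 0.666.
- n = 30: r = 9 gives 0.885; r = 8 gives 0.783.

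These match Table 1. The planned maximum does not enter the formula.

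**Table 2.** Let f10 = P(X10 ≥ 4), f20 = P(X10 ≤ 3, X20 ≥ 6) and f30 = P(X10 ≤ 3, X20 ≤ 5, X30 ≥ 9), by exact binomial recursion. Pause probability = f10 + f20 + f30. Average size = 10 f10 + 20 f20 + 30 f30 + 40 (1 − sum).

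| True rate | f10 | f20 | f30 | Sum | Average size |
|---|---|---|---|---|---|
| 0.10 | 0.0128 | 0.0072 | 0.0005 | 2.05% | 39.5 |
| 0.15 | 0.0500 | 0.0408 | 0.0064 | 9.73% | 37.6 |
| 0.20 | 0.1209 | 0.1109 | 0.0262 | 25.79% | 33.9 |
| 0.25 | 0.2241 | 0.1976 | 0.0555 | 47.73% | 28.8 |
| 0.30 | 0.3504 | 0.2660 | 0.0756 | 69.20% | 23.4 |

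(Sums are from unrounded terms.) At 0.30 the average size is 3.50 + 5.32 + 2.27 + 40 × 0.308 = 23.4. The plan's table is reproduced.

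**Smaller maxima.** Keep only looks that fall before the maximum:

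| Maximum counted | Looks able to pause | 0.10 | 0.15 | 0.20 | 0.25 | 0.30 |
|---|---|---|---|---|---|---|
| 31–40 | 10, 20, 30 | 2.1% | 9.7% | 25.8% | 47.7% | 69.2% |
| 21–30 | 10, 20 | 2.0% | 9.1% | 23.2% | 42.2% | 61.6% |
| 11–20 | 10 | 1.3% | 5.0% | 12.1% | 22.4% | 35.0% |
| 10 or fewer | none | 0 | 0 | 0 | 0 | 0 |

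For 21–30 the differences at 0.20 / 0.25 / 0.30 are 2.6, 5.6 and 7.6 points. For 11–20 the probability is about half the stated value at those rates.

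**Which band applies.** The 20 to 40 in SAP 2.3 and the 40 in Table 1 need not be the same count. The former sits in a pooled-by-dose paragraph; the rule speaks of dose expansion and new subjects. As an illustration, assume 46 enrolled, 6 run-in subjects at each of two doses and k optimization subjects per dose:

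- expansion = 46 − 12 − 2k = 34 − 2k;
- pooled at the final dose = 6 + k + (34 − 2k) = 40 − k.

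Then k = 0 gives 34 in expansion (three looks), k = 5 gives 24 (two looks; 35 pooled), k = 10 gives 14 (one look; 30 pooled) and k = 12 gives 10 (no look; 28 pooled). If only expansion subjects count, the one-look case can therefore arise at a mid-range pooled total.

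**Exposure.** Expected subjects with an event at a true rate of 0.30 = 0.30 × average size: 0.30 × 23.4 = 7.0 for a maximum of 40, 0.30 × 20.3 = 6.1 for 30 and 0.30 × 16.5 = 5.0 for 20.

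**The case for a change.** The best argument for acting is that disclosure is nearly free. Dose optimization is written into the design, it draws on the same pool as expansion, and neither document states outright whether run-in or optimization subjects at the selected dose are counted. With the same trial giving response-rate precision at 20 and 40, safety performance at 40 alone is lopsided. At a true rate of 0.30, 69.2% against 35.0% is a real difference.

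These facts stand, including the silence on who is counted. They do not show that the rule misfires. The posterior criterion uses the prior, the subjects counted and their events; it is valid at each look whatever the final size. Either count can be applied sensibly, and the wording leans towards expansion subjects. A pause that never comes because enrolment has ended is not a failure to stop enrolment, and fewer people are then exposed. If a look is also made at the maximum itself, the chance of crossing and triggering review equals the stated figures for 30 and is 61.6% at a true rate of 0.30 for 20. At true rates of 0.10 and 0.15 fewer pauses are welcome, so 40 is not uniformly the favourable case. ISMC review about every 3 months (Protocol 8.3.6.2), with ad hoc reviews allowed, runs independently of these looks.

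**Conclusion.** No change is needed. Table 2 is correct for the 40-subject course that the adjoining table displays, and its pause probabilities hold for any maximum of 31 to 40. That covers every expansion without dose optimization (34 to 40); only the average sizes fall, for example from 33.9 to 29.4 at a true rate of 0.20 with a maximum of 34. If optimization takes subjects, the pause probability at rates 0.20 to 0.30 drops by 2.6 to 7.6 points for a maximum of 21 to 30, to roughly half for 11 to 20, and to zero for 10 or fewer.

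These figures rest on looks every 10 counted subjects, made while expansion is still enrolling. The band also depends on who is counted, which an analyst can settle from the wording when applying the rule. A label on the table, more rows or a counting sentence would be optional explanation. The boundaries, the criterion, enrolment and the trial's conclusions would be the same with or without them.
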